# B. Secondary Specimen Collection

Not applicable

#### 1.9 Data Collection

# A. Primary Data Collection

Location: For recruitment at the USF COVID testing center and Rutgers University medical schools, participants' name and contact details will be obtained from the testing schedules at the USF Carol & Frank Morsani Center for Advanced Healthcare drive-through testing center. Participants' sex, date of birth, race/ethnicity, habitual prebiotics/probiotics consumption, medical history and medications will be collected during the self-administered preliminary screening survey and eligibility screening interview on Castor. For online recruitment and recruitment through Vault Health company, individuals who express interest in participating in the study will provide their email addresses in the landing page of the study to access a screening survey and allow communications with the research team. All information necessary for establishing eligibility and confirming enrollment will be collected in the

Protocol Title: COVGUT20

online self-administered preliminary screening survey and during the informed consent interview. Name and phone number of study candidates will be collected on the HIPPA compliant software Castor if they passed screening survey. Home addresses will be collected over a phone call with the research team. During the study, all participants will record objective and subjective symptoms, adverse events, medication changes, NBT-NM108 (treatment group) and water (control group) consumption at home and report to the research team.

- Process of Data Collection: For recruitment at the USF COVID testing center, prospective participants will be identified from individuals who have scheduled an appointment at the USF Carol & Frank Morsani Center for Advanced Healthcare drive-through testing center for COVID-19 testing. Study coordinators will call those who appear to be eligible to introduce the study. Potential study candidates who express interest will complete an online self-administered preliminary screening survey (Appendix 2) and then attend an online consent and screening interview with the study coordinator on Castor if they pass the preliminary screening survey. During the eConsent interview, the study coordinator will first confirm that the study candidates continue to experience COVID-19-like symptoms as reported in the preliminary screening survey. Then an electronic informed consent will be obtained and the study coordinator will ask a set of pre-determined questions to collect the patient's medical history and other necessary information to establish eligibility (Appendix 4). Female prospective participants of child-bearing age will be provided with a pregnancy test kit. They will perform the test at home and upload a picture of result to the research team via Castor. For online recruitment and recruitment through Vault Health company, individuals who are interested in participating in the study will provide their email addresses on the landing page of the study (Appendix 19) to get access to an online self-administered preliminary screening survey (Appendix 22). They will provide their demographics and medical information for the research team to evaluate the severity of COVID-19-like symptoms. If the study candidates appear to be eligible for the study, they will be instructed to provide their name and phone number on the HIPPA compliant software Castor and schedule an online consent interview. The research team will contact the study candidates over the phone to confirm their details and collect their home addresses to ship study supplies. Female study candidates who are of child-bearing age will be provided with a pregnancy test kit and complete the test prior to the consent interview. During the eConsent interview, the study coordinator will first confirm that the study candidates continue to experience COVID-19-like symptoms as reported in the preliminary screening survey. Then an electronic informed consent will be obtained and the study coordinator will ask a set of pre-determined questions to collect the patient's medical history and other necessary information to establish eligibility (Appendix 4). During the study, all participants will use the provided thermometer, glucometer (if the participant has T2DM), and pulse oximeter to measure body temperature (oral), fasting blood glucose (if the participant has T2DM), pulse rate and oxygen saturation level, record respiratory rate, symptoms, adverse events, medication changes and consumption of NBT-NM108 (treatment group) and water (control group) at home. They will record the data in the participant booklet (Appendices 8.1 and 8.2) and report the data to the research team on Castor (Appendices 9-11).
- Timing and Frequency: Prospective participants will complete one online self-administered preliminary survey and attend one virtual eligibility screening interview. All enrolled participants will record objective and subjective symptoms, adverse events and medication changes twice a day (in the morning after at least 8 h of overnight fasting at around 8 am and 2 h after dinner at around 8 pm) and fasting blood glucose (if the participant has T2DM) and intervention compliance once a day from Day 1 to Day 28 or until they recover from COVID-19-like illness (whichever is later). After they recover, they will record these data once a week until Day 56 (i.e. the mornings of Days 35, 42, 49 and 56 as appropriate). Participants will also record these data on the day that they recover from COVID-19-like illness (if before Day 56). If participants are hospitalized during the study, they will discontinue all data collection by themselves during hospitalization but relevant clinical data will be retrieved from the hospital medical records. If participants are discharged on or before Day 56, they will record objective and subjective symptoms, adverse events and medication changes twice a day (in the morning after at least 8 h of overnight fasting around 8 am and 2 h after dinner around 8 pm) and fasting blood glucose (if the participant has T2DM) once a day until they recover from COVID-19-like illness and thereafter record these data once a week until Day 56.

Protocol Title: COVGUT20

- Procedures for Audio/Visual Recording: Not applicable
- Study Instruments: Self-administered preliminary screening surveys (Appendices 2 and 22) and a screening checklist (Appendix 4) will be used during the eligibility screening interview to collect information necessary to determine eligibility. A booklet (Appendices 8.1 and 8.2) will be provided to all enrolled participants which will include the study schedule, instructions for using the thermometer, pulse oximeter and glucometer, instructions for intervention, sample collection and shipment. The booklet will also include instructions and tables for participants to record fasting blood glucose (if the participant has T2DM), objective and subjective symptoms, medication changes, adverse events, and intervention compliance. Participants will report these data to the study team on Castor, a cloud-based clinical data management platform (Appendices 9-11). Participants will have access to an interactive online personal dashboard to review their study progress and the data that they have reported (Appendix 17). Participants will have access to a series of videos that provide an overview of the study, how to complete the preliminary screening survey and what is required of them during the study (Appendix 16). A stool sample description form (Appendix 12) will be provided to the participants to describe the fecal sample based on the Bristol Stool Scale [17]. Written step-by-step instructions will be provided for the participants to ship the fecal samples to the research team (Appendix 18).
- Ethnographic Studies, Interviews, Or Observation: Not applicable
- Subject Identifiers: For recruitment at the USF COVID testing center and Rutgers University medical schools, subject identifiers (name, date of birth, phone number, email and home address) will be retrieved from the testing schedules at the USF Carol & Frank Morsani Center for Advanced Healthcare drive-through testing center and testing center at Rutgers University medical schools and collected during the eConsent and eligibility screening interview. For online recruitment and recruitment through Vault Health company, individuals who are interested in the study will provide their email addresses on the landing page of the study for the research team to initiate contacts. Date of birth will be collected in the online self-administered screening survey. Name and phone number will be collected on castor and in the HIPPA compliant scheduling software 10To8. Home address will be collected over the phone by the study coordinators if the study candidates appear to be eligible for informed consent and the next stage of screening. This information is only used to establish eligibility and schedule supplies shipment and follow-up phone calls. Participants will provide their social security number as per Internal Revenue Service (IRS) reporting requirements if they agree to receive participant compensation via the ClinCard. No identifiers will be collected in other study instruments.

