INFORMED CONSENT AND ELIGIBILITY SCREENING PART 2. The informed consent process will be conducted via Castor's eConsent video call module. At the beginning of the call, the study coordinator will confirm that the study candidates continue to experience the COVID-19-like symptoms reported in the preliminary screening survey, thereafter the study coordinator will explain the rationale, aim, expected outcomes and significance of the research, the experimental procedures, what is required from the participants, and the benefits and risks associated with the study. Electronic informed consent will be obtained during the interview prior to further eligibility screening (Appendices 3 and 4). A consent for health information release (Appendix 3) will also be obtained during informed consent procedure. After the study candidates sign the electronic informed consent documents, the study coordinator will ask some additional questions regarding their medical history and other conditions to establish eligibility (Appendix 4). In the case of study candidates who are recruited online, they will also be asked to provide electronic proofs of a positive/pending COVID-19 test (Appendix 24) and a negative pregnancy test result (if appropriate; Appendix 6) during the interview. This consent and eligibility screening interview will take a maximum of 60 minutes to complete.

**ENROLLMENT.** The study physicians will review all screening data and determine if the study candidates are suitable for home isolation and confirm enrollment.

**RANDOMIZATION AND ALLOCATION CONCEALMENT.** Enrolled participants will be randomized to the control or treatment group at a 1:1 ratio, using randomization via a dynamic minimization to minimize imbalance between groups over factors including COVID-19-like illness severity (mild vs moderate), the use of COVID-19 vaccination or other treatments that may reduce severity such as monoclonal antibody treatment vs. not used, age (≤60 vs >60 years) and gender (male vs female) [16]. When imbalance is detected, the new patient will be allocated with probability 0.7 vs 0.3. When the treatment assignments are at balance, the patient will be allocated with probability 0.5 vs 0.5. The randomization will be performed

via a closed source app written by one of the Co-PI. The investigator who uses the app will only know the allocation result, i.e., control or treatment group, of the new patient.

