## D. Endpoints

- 1. Primary outcome:
  - Gut microbiota composition
- 2. Secondary outcomes:
  - At Days 1, 14, 28 and 56:
  - a) Outcome of COVID-19-like illness (hospitalization or death)
  - b) Proportion of participants who are "alive and not admitted to the hospital"
  - c) Proportion of participants who visit the emergency room
  - d) Proportion of participants who have complete resolution of all objective symptoms, i.e. all vital signs are within the normal range for at least 48 h, including body temperature (oral) 36.5-37.5°C (97.7-99.5°F), pulse rate 60-100/min, respiratory rate 12-20/min and oxygen saturation level at 95-100%
  - e) Proportion of participants who have complete resolution of subjective symptoms, i.e. absence of all COVID-19-like symptoms listed by CDC (updated May 13, 2020) for at least 48 h, including the presence of chills or "feeling feverish", cough, shortness of breath or difficulty breathing, fatigue, muscle or body aches, headache, new loss of taste or smell, sore throat, congestion or runny nose, nausea or vomiting and diarrhea
  - f) Proportion of participants who have complete resolution of subjective symptoms except fatigue and cough, i.e. absence of all COVID-19-like symptoms listed by CDC (updated May 13, 2020) for at least 48 h, including the presence of chills or "feeling feverish", cough, shortness of breath or difficulty breathing, fatigue, muscle or body aches, headache, new loss of taste or smell, sore throat, congestion or runny nose, nausea or vomiting and diarrhea
  - g) Illness severity based on the categorization from FDA [18] and the Ordinal Scale for Clinical Improvement from the World Health Organization [19]
  - h) Body temperature (oral)
  - i) Oxygen saturation level
  - i) Pulse rate
  - k) Respiratory rate
  - I) Fasting blood glucose
  - Time to complete resolution of all objective symptoms
  - Time to complete resolution of all subjective symptoms
  - Time to complete resolution of all subjective symptoms except fatigue and cough

Protocol Title: COVGUT20

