#### 6.0 Data Management Plan

#### 6.1 Data Analysis

DNA, protein, and metabolites will be extracted from fecal samples. 16S rRNA gene V4 region sequencing and metagenomic shotgun sequencing with different platforms such as Ilumina and PacBio will be done using the extracted DNA. Metaproteome profiling will be achieved using mass spectrometry-based proteome analysis based on extracted protein. Metabolomics will be measured using fecal sample supernatant. Multiomics data will be combined with clinical data for statistical analysis to explore the overall changes during COVID-19 course and changes induced by the treatment.

16S rRNA gene sequencing data will be analyzed based on the amplicon sequence variants (ASVs) [28] to determine the gut microbiota composition using QIIME 2 [29]. Shannon index and ASV richness will be used to assess alpha diversity. Principal coordinate analysis will be used to compare and visualize dissimilarity in gut microbiota structure between samples based on beta diversity (Weighted and Unweighted UniFrac distance) and statistical differences will be tested using permutational multivariate analysis of variance (PERMANOVA). PICRUSt 2 will be used to predict the functions of individual ASVs and the collective functions of the gut microbiota at the gene content and pathway levels [30]. Global functional profiles of the gut microbiota will be compared and visualized by principal component analysis.

Metagenomic sequencing data will be analyzed in a genome-centric way. The raw sequencing data will be processed with KneadData (https://huttenhower.sph.harvard.edu/kneaddata) for quality control. High quality draft genomes will be de novo assembled from the high-quality sequencing data. The quality assessment, taxonomic assignment and functional annotation of the genomes will be conducted by using CheckM [31], GTDB-Tk [32] and Prokka [33] respectively. Principal coordinate analysis will be used to compare and visualize dissimilarity in gut microbiota structure between samples based on beta diversity and statistical differences will be tested using permutational multivariate analysis of variance (PERMANOVA).

Protocol Title: COVGUT20

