STATISTICAL ANALYSIS PLAP

TUDY TITLE: MODULATION OF GUT MICROBIOTA WITH NBT-NM108 AS AN ARLY TREATMENT FOR SUSPECTED OR CONFIRMED COVID-19 ATIENTS HORT NAME: COVGUT20 ROTOCOL ID: NBTNM10810012020 ;LINCIALTRIALS.GOV ID: NCT04540406

his document is confidential. It contains proprietary information of Notitia Biotechnologie ny viewing or disclosure of such information that is not authorized in writing by the Spons trictly prohibited. Such information may be used solely for the purpose of reviewing or erforming this study

Study Analysis Plan

Sequencing Data Analysis

DNA, protein, and metabolites will be extracted from fecal samples. 16S rRNA gene V4 region sequencing and metagenomic shotgun sequencing with different platforms such as Ilumina and PacBio will be done using the extracted DNA. Metaproteome profiling will be achieved using mass spectrometry-based proteome analysis based on extracted protein. Metabolomics will be measured using fecal sample supernatant. Multi-omics data will be combined with clinical data for statistical analysis to explore the overall changes during COVID-19 course and changes induced by the treatment.

16S rRNA gene sequencing data will be analyzed based on the amplicon sequence variants (ASVs) [1] to determine the gut microbiota composition using QIIME 2 [2]. Shannon index and ASV richness will be used to assess alpha diversity. The principal coordinate analysis will be used to compare and visualize dissimilarity in gut microbiota structure between samples based on beta diversity (Weighted and Unweighted UniFrac distance). Statistical differences will be tested using permutational multivariate analysis of variance (PERMANOVA). PICRUSt 2 will be used to predict the functions of individual ASVs and the collective functions of the gut microbiota at the gene content and pathway levels [3]. Global functional profiles of the gut microbiota will be compared and visualized by principal component analysis.

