Metagenomic sequencing data will be analyzed in a genome-centric way. The raw sequencing data will be processed with KneadData (https://huttenhower.sph.harvard.edu/kneaddata) for quality control. High-quality draft genomes will be de novo assembled from the high-quality sequencing data. The quality assessment, taxonomic assignment, and functional annotation of the genomes will be conducted by using CheckM [4], GTDB-Tk [5], and Prokka [6] respectively. The principal coordinate analysis will be used to compare and visualize dissimilarity in gut microbiota structure between samples based on beta diversity, and statistical differences will be tested using permutational multivariate analysis of variance (PERMANOVA).

The metaproteomes will be analyzed by using Unified Human Gastrointestinal Genome (UHGG) v2.0 as the reference for functional annotation and protein sequences database. The predicted protein sequences from metagenomic dataset will be aligned with the measured protein sequences from metaproteomic dataset for integrative analysis. Global level protein changes of the gut microbiota will be compared and visualized by principal component analysis. The metabolome will measure both polar metabolites and lipids. Global level of compound changes of will be compared and visualized by principal component analysis.

Repeat measures correlation will be used to assess the relationships between ASVs/highquality draft genomes [7], followed by ASV/high-quality draft genome clustering based on co-abundance patterns. Multivariate methods such as MaAsLin2, that allow adjustment for confounding variables and model the covariates as random effects, will be applied to interpret the relationship between ASVs / ASV co-abundance groups/functions/high-quality draft genome co-abundance groups and the clinical metadata/proteins/metabolites.

Clinical Data Analysis

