
outcomes (e.g., illness severity, body temperature (oral), and oxygen saturation level, etc.) will be modeled using linear mixed models, and death, reported adverse event, or other appropirate competing risk will be modelled using Weibull proportional hazards model [16]. Age, gender, race/ethnicity, baseline COVID-19 severity, and whether the participant has taken treatments that may reduce COVID-19 severity (vaccination and monoclonal antibody treatment) will be controlled as covariates in these statistical analyses, where appropriate. Within-group changes of main outcomes between groups will be modeled as change from pre- to post-treatment usng ANOVA and modeled as the post-treatment value as the change itself with the pretreatment value entered as covariate using ANCOVA [17]. Lastly, alternative statistical methods will be explored to quantify the underlying differences between groups with respect to a time-to-event end point, robust methods include calculating ratio/difference of t-Year Survival Rates, ratio/difference of percentiles of survival functions, and ratio/differenceof restricted mean survival times or restricted mean time lost [18]. Statistical analyses described above will be conducted for both intentto-treat dataset and per-protocal dataset. For each test of an outcome, we define the statistical significance by p<0.05. The false discovery rate [19] will be applied for multiple testing, where appropriate. Sensitivity analysis using multiple imputation methods [20] will be performed to handle the missing data. Other approaches, such as methods of selection models [21] or use the pattern-mixture models such as the control-based pattern imputation approach, or the tipping-point approach [22, 23] will also be considered.

Reference

- 1. Callahan, B.J., et al., *DADA2: High-resolution sample inference from Illumina amplicon data.* Nat Methods, 2016. **13**(7): p. 581-3.
- 2. Bolyen, E., et al., QIIME 2: Reproducible, interactive, scalable, and extensible microbiome data science. 2018, PeerJ Preprints.
- 3. Douglas, G.M., et al., *PICRUSt2: An improved and extensible approach for metagenome inference.* bioRxiv, 2019: p. 672295.
- 4. Parks, D.H., et al., *CheckM: assessing the quality of microbial genomes recovered from isolates, single cells, and metagenomes.* Genome Res, 2015. **25**(7): p. 1043-55.
- 5. Chaumeil, P.A., et al., *GTDB-Tk: a toolkit to classify genomes with the Genome Taxonomy Database.* Bioinformatics, 2019.

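### The PERMANOVA for the primary outcome is specified with no baseline terms, not even the four factors on which allocation is minimized

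*Protocol*

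**What the plan says.** - **Outcome.** Protocol 1.3 D gives one primary outcome, "Gut microbiota composition". Stool is collected at Days 0, 28 and 56 and on the day of recovery (1.3 B).
- **Test.** Protocol 6.1, for 16S data on weighted and unweighted UniFrac distances: "statistical differences will be tested using permutational multivariate analysis of variance (PERMANOVA"). The SAP's Sequencing Data Analysis section repeats this, and the metagenomic PERMANOVA is described in the same way. No time point, model term, baseline adjustment or permutation scheme is given.
- **Allocation.** Protocol 1.3 A uses dynamic minimization (probability 0.7 vs 0.3) on illness severity, vaccination or other severity-reducing treatment, and "age (≤60 vs >60 years) and gender (male vs female").
- **Clinical models.** The SAP's Clinical Data Analysis section names its covariates: "Age, gender, race/ethnicity, baseline COVID-19 severity, and whether the participant has taken treatments that may reduce COVID-19 severity (vaccination and monoclonal antibody treatment"). It also has a change analysis "with the pretreatment value entered as covariate using ANCOVA".
- **Feature-level analysis.** The SAP plans "Multivariate methods such as MaAsLin2, that allow adjustment for confounding variables and model the covariates as random effects", without naming the confounders.
- **Habitual supplement use.** Protocol 1.9 A, in its account of USF and Rutgers recruitment: "habitual prebiotics/probiotics consumption, medical history and medications will be collected during the self-administered preliminary screening survey". Neither document mentions it again.

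**The concern.** The secondary clinical outcomes have a prespecified covariate set that covers the minimization factors. The single primary outcome has none.

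Minimization forces the arms to be alike on four factors. If those factors explain part of composition, the arm difference varies less than an unrestricted permutation of labels supposes. The reference distribution is then too wide and the test is conservative. The variation due to the factors also stays in the error term.

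The planned effect is small (omega-squared 0.0106 to 0.0120, Protocol 1.5), so lost precision matters. An unspecified formula also leaves covariates, time point and handling of repeated samples open to choice after the data are seen.

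**Working it through.** **1. The plan's own figure.** Protocol 1.5 states 80% power with 16 per group at omega-squared 0.0106. This cannot be reproduced, because the within-group distance mean and SD are unpublished. As a stand-in, treat composition as p equal-variance dimensions and use a noncentral F with df1 = p, df2 = p(N − 2) and λ = pN·ω²/(1 − ω²).

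- p = 1, N = 32: power 8.8%.
- p = 140: λ = 140 × 32 × 0.0106/0.9894 = 48.0, df = 140 and 4,200, power 80.0%.

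The value 140 is calibrated to the stated power, so this does not confirm the plan's figure.

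**2. The minimization factors.** The simulation used 32 participants, four balanced binary factors, 0.7/0.3 minimization, 140 dimensions, ω² = 0.0106, 1,000 trials per cell and 199 permutations. R² is the share of composition that the factors explain together. It is assumed, because the documents do not give it. Each cell shows rejection rate under the null / power, in %.

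| R² | Unadjusted | Adjusted, residuals permuted under the reduced model | Adjusted, minimization re-run |
|---|---|---|---|
| 0 | 4.8 / 77.8 | 3.2 / 59.9 | 4.7 / 71.1 |
| 4% | 2.5 / 73.1 | 1.8 / 63.7 | 4.6 / 76.2 |
| 8% | 1.5 / 60.8 | 2.1 / 65.2 | 5.2 / 77.2 |
| 20% | 0.7 / 22.7 | 2.8 / 80.3 | 5.4 / 87.8 |

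Monte Carlo error is about ±3 points for power near 75% (1.96 × √(0.75 × 0.25/1,000) = 0.027). A separate simulation of the same kind put the unadjusted null rate at about 1% to 4%. In it, adjustment raised power from 75% to 77% at R² 4% and from 70% to 81% at 8%.

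The direction is consistent: ignoring the factors makes the test conservative, increasingly so as R² rises. The size of the gain depends on the permutation scheme. With so many dimensions and so few participants, permuting reduced-model residuals is itself conservative. In the table it loses to the unadjusted test at 4% and overtakes it by 8%.

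**3. Habitual prebiotic/probiotic use.** For one covariate, divide the effect by (1 − R²) and use df2 = p(N − 3). At R² 0.01 / 0.02 / 0.05 / 0.10 (assumed), power is 80.6 / 81.2 / 83.0 / 85.9%. This variable is not minimized, so its chance correlation with arm costs about 1/(N − 1) = 1/31 of the arm's variation. Charging that gives 78.6 / 79.2 / 81.1 / 84.2%. Against 80.0%, the change runs from a loss of 1.4 points to a gain of 4.2.

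**4. Day 0 composition.** As a single term at an assumed R² of 0.3 or 0.5, the same formula without the 1/31 charge gives 95.7% or 99.7%. Several principal coordinates would use more degrees of freedom.

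**The case against.** **Randomization protects validity, and the trial is exploratory.** Both are true. Chance imbalance is already part of what the p-value allows for, and a conservative test does not produce false positives. What stands against the plan is lost precision and an unspecified formula.

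**Adjustment is provided elsewhere.** The MaAsLin2 clause concerns feature-level associations, with confounders unnamed. The ANCOVA sentence is in the clinical section and cannot define terms for a distance-matrix test. Neither fills the gap. The MaAsLin2 clause does mean that habitual use is named in no model, which is weaker than saying it will enter none.

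**Adjustment is not always a gain.** This stands. If the factors are unrelated to composition, adjustment costs power (77.8% to 71.1% in the table, more with permuted residuals). The simulation also minimizes all 32 participants. The trial minimizes 100 and bases power on the confirmed cases, so balance within that subset, and with it the conservatism, would be weaker.

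**A stronger reading is tempting.** A reader might infer that unadjusted supplement use confounds the primary comparison because it resembles the intervention. If 30% were users (assumed), the 95% range of the arm difference in users at 20 per arm is ±1.96 × √(0.3 × 0.7 × 2/20) = ±28 points. That is a share of participants and not a distance in composition. An imbalance of that size gives arm a share of R² × 1.96²/(2 × 20) = 0.096 × R². If habitual use explained as much as the full high-fiber intervention in Protocol 1.5 (R² 0.0120, assumed), this is 0.0012 against a planned 0.0106. The variable also pools prebiotics with probiotics, and the documents give no dose or duration. They do not support a claim of bias.

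**Conclusion.** The concern holds as a matter of precision and prespecification, not of bias. The primary PERMANOVA omits four factors that governed allocation and are adjusted for in the secondary models.

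With the factors explaining an assumed 4% to 20% of composition, the unadjusted test ran at about 1% to 4% instead of 5%. Adjusting gained about 2 to 3 points of power at 4% and 11 to 16 points at 8%, given a permutation scheme that holds its level. These figures rest on assumed R², 140 calibrated dimensions and minimization applied to exactly the participants tested. They show direction and rough size only.

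Habitual prebiotic/probiotic use is a minor part of the point, because its expected effect on power is a few points in either direction. Nor can it be taken as available for everyone. Protocol 1.9 A states its collection alongside USF and Rutgers recruitment. For online and Vault recruits it promises only what eligibility and enrollment require, and the survey appendices are not in the public documents.

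**What to change.** Add to the SAP, before any microbiota data are examined by arm:

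1. One between-arm PERMANOVA per named distance, with one sample per participant at a named post-baseline time point such as Day 28.
2. Arm tested as the marginal (last) term after severity, vaccination or other treatment, age group and gender.
3. A named permutation scheme. Permuting residuals under the reduced model is the simple choice, but check its level by simulation at the trial's actual size. Re-running the minimization with factors and entry order held fixed kept close to 5% here and is the natural alternative.
4. Day 0 composition, for example its leading principal coordinates, as a further baseline term if the sponsor accepts the degrees of freedom it uses.
5. A sensitivity analysis adding habitual prebiotic/probiotic use, after confirming that the online and Vault surveys record it as well as USF/Rutgers.
6. The covariates for MaAsLin2, by name.

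For the minimization factors this is a free improvement: they are recorded for everyone because they drive allocation, so no participants, samples or visits are added. The one cost is some power if they turn out to be unrelated to composition. Item 4 uses degrees of freedom, and item 5 may need a check for missing data.
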